1.2.5.2 Injection Site Reactions

In a repeat-dose GLP toxicology study in Cynomolgus monkeys, BOS161721 was administered every 2 weeks by IV or SC (50 mg/kg) for 3 months (a total of 7 doses); no SC animals had injection reactions.

Based on the Phase 1 SAD study (BOS161721-01), incidence of injection site reactions in subjects who received BOS161721 was similar to placebo.

Patients will be monitored for local injection site reactions in this study. See [Section 7.2.7](#).

1.2.5.3 Immune Complex Disease

The potential risk of immune complex disease for BOS161721 is theoretical, based on the known risks associated with mAbs. The administration of a mAb can result in the formation of ADAs. Administration of the mAb in the presence of ADA may result in the formation of circulating antibody-antigen complexes potentially resulting in altered BOS161721 levels or activity or deposition of the complexes in microvasculature. Complement is frequently involved in the latter setting, and the breakdown products of complement attract polymorphonuclear leukocytes to the site of deposition where they can provoke local tissue damage through specific or nonspecific release of enzymes. Two of the more common end-organ targets are the blood vessels (vasculitis) and kidney (nephritis). These clinical manifestations represent immune complex disease or Type III hypersensitivity. Although BOS161721 is a humanized mAb, ADAs may develop; however, the likelihood of occurrence of immune complex disease with BOS161721 is low. The findings of immune complex disease are typically reversible when mAb administration stops and the antibody-antigen complexes are cleared from the body.

Based on the limited Phase 1 SAD study (BOS161721-01), immune complex disease in subjects who received BOS161721 was not observed.

1.2.5.4 Infections

BOS161721 is expected to diminish the activity of T-cell, B-cell and NK-cell lines. Like other medications modulating immune response, BOS161721 may increase the potential risk for infection, including serious infections. IL-21 produced by CD4⁺ Th cells is required to sustain the anti-viral function of CD8⁺ T-cells against chronic viral infections. Nonclinical evidence suggests that the risk of chronic viral infection recurrence or increased severity may occur with IL-21 inhibition.³⁵

These conditions will be fully characterized with clinical descriptions and routine laboratory and/or specialty testing and treated where indicated with appropriate local standard of care.

Patients with a history of opportunistic infection, including recurrent or severe disseminated herpes zoster or disseminated herpes simplex within the last 3 years, or any other underlying pathology predisposing to serious infection, are excluded from studies with BOS161721 (for further details please refer to the current IB for BOS161721).

Patients will be assessed for hepatitis B, and C, and HIV-1/2 combination, at screening.

Cryptosporidium Infection

Cryptosporidium infection was noted in patients with an IL-21 receptor loss-of-function gene mutation and similar findings of cryptosporidium infection have been observed in immunosuppressed liver transplant and human immunodeficiency virus patients.^{36,37} Since

BOS161721 is expected to diminish the immunosurveillance activity of T-cell, B-cell, and NK-cell lines, a similar risk is biologically plausible with prolonged exposure to BOS161721.

Since the risk of opportunistic cryptosporidium infection increases with low levels of CD4+ T-cells,³⁷ patients with a CD4+ count $< 500 \text{ cell/mm}^3$ were excluded from the Phase 1 SAD study (BOS161721-01), and will be excluded from the proposed MAD/POC studies. Patients exposed to investigational product who develop diarrhea during the course of the study should immediately undergo an assessment for opportunistic infection including stool for ova and parasites and stool examination for cryptosporidium. Positive cryptosporidium in stool sample at screening is an exclusion. Treatment by the investigator where indicated should be guided by findings and be consistent with local standard of care.

Based on the limited Phase 1 SAD study (BOS161721-01), infections in subjects who received BOS161721 was not observed.

1.2.5.5 Malignancy

The stimulatory effect of IL-21 on NK cells and CD8+ T-cells suggests the cytokine may have anti-tumor activity. Nonclinical studies have demonstrated significant anti-tumor effects of IL-21 in a number of tumor models. IL-21 therapy of human metastatic melanoma and renal cell carcinoma has demonstrated POC with significant increases in levels of perforin, granzyme B, and interferon gamma (IFN γ) expression in CD8+ T-cells and NK T-cells. Clinical response has been limited in these generally unmanageable diseases.

The impact of treatment with anti-IL-21 therapy on the development or growth of malignancies is not known; however, as with other immunomodulatory biologic agents, treatment with BOS161721 may result in an increase in the risk of malignancies. NK cell suppression by IL-21 neutralization may represent a biological mechanism for a potential risk for malignancy. Patients with a history or current diagnosis of cancer within the past 5 years, with the exception of non-melanoma skin cancer or cervical cancer in situ treated with apparent success with curative therapy, are excluded from the study.

Based on the limited Phase 1 SAD study (BOS161721-01), malignancy in subjects who received BOS161721 was not observed.

1.2.5.6 Hepatic Function Abnormality

There is no substantial evidence suggesting BOS161721 is associated with liver function abnormality. However, as a precaution, patients with a history of abnormal alanine aminotransferase (ALT) and/or aspartate aminotransferase (AST), or bilirubin at screening (ALT/AST $> 2 \times$ upper limit of normal [ULN]; total bilirubin $> 1.5 \times$ [ULN] and judged by the investigator to be clinically significant) were excluded from the Phase 1 SAD study (BOS161721-01), and will be excluded from the MAD study. Patients with a positive hepatitis B or C test or a history of alcohol dependence will also be excluded.

Based on the limited Phase 1 SAD study (BOS161721-01), hepatic function abnormality in subjects who received BOS161721 was not observed.

1.2.5.7 Failure of Vaccination

IL-21 is a key cytokine in development of B-cells into immunoglobulin-secreting plasma cells. Abnormal signaling through the IL-21R/Janus Kinase (JAK)3/signal transducer and activator of transcription (STAT3) pathway leads to defective humoral immune responses to both T-dependent and T-independent antigens and impairs the establishment of long-lasting B-cell memory. Abnormal signaling through the pathway has been related to decreased specific antibody responses following vaccination, and to increased susceptibility to encapsulated bacterial infections.³⁸

The effect of BOS161721 was evaluated in in vivo single dose studies in Cynomolgus monkey in which the animals received vaccination to T-cell dependent KLH antigen to stimulate a TDAR. These in vivo studies demonstrated that BOS161721 significantly inhibited B-cell proliferation and IgG antibody responses to the KLH protein antigen; however, it is worth noting that BOS161721 administration did not produce any remarkable changes in anti-KLH antibody data for IgM, IgG1, IgG3, and IgG4 or anti-tetanus toxoid (TT) antibody data for IgM, IgG, IgG1, or IgE during the dosing phase in the same study.

1.2.5.8 Potential for Drug-Drug Interactions

Drug-drug interactions were not evaluated in the Phase 1 SAD study (BOS161721-01), which included only healthy adult subjects. Use of prescription medications (with the exceptions of oral contraceptives), and over-the-counter (OTC) treatments including herbal supplements such as St John's Wort (except multivitamins), in the 2 weeks prior to screening was prohibited in the SAD study.

See [Section 5.5](#) for other specific exclusion criteria which support lowered risk of interactions, and [Section 5.6.1](#) for corticosteroid (CS) dosing. In addition, [Section 1.2.5.6](#) describes considerations for hepatic function for this study.

1.2.5.9 Potential Risk to Fetal Development

No data on preclinical reproductive toxicity are available at the time of this study.

2 STUDY OBJECTIVES

This trial has separate primary and secondary objectives for the MAD Phase 1b and POC Phase 2 studies.

2.1 Phase 1b Multiple Ascending Dose

2.1.1 Primary Objective

To assess safety, tolerability, and immunogenicity of repeat doses of BOS161721 (20 mg, 60 mg, and 120 mg) administered SC in adult patients with moderately to severely active SLE on limited background standard of care treatment, in order to estimate the optimal dose.

2.2 Phase 2 Proof of Concept

2.2.1 Primary Objective

To demonstrate a superior effect of BOS161721 at the chosen dose compared with placebo for response on the SLE Responder Index 4 (SRI-4), with sustained reduction of oral CS, in adult patients with moderately to severely active SLE on limited background standard of care treatment.

2.2.2 Secondary Objectives

To demonstrate a superior effect of BOS161721 at the chosen dose compared with placebo for response on clinical indicators of SLE activity, in adult patients with moderately to severely active SLE on limited background standard of care treatment, including:

- Changes in SLE-specific autoantibody titers
- Changes in complement 3 and 4 (C3 and C4) levels
- Responses on SRI-4, SRI-5, and SRI-6, with sustained reduction of oral CS
- Response on the British Isles Lupus Assessment Group (BILAG)-based Composite Lupus Assessment (BICLA)
- Response on the Cutaneous Lupus Erythematosus Area and Severity Index (CLASI)
- Changes in the SLE Disease Activity Index 2000 (SLEDAI-2K)
- Changes in American College of Rheumatology (ACR)-28 joint count

3 STUDY ENDPOINTS

This trial has separate primary and secondary endpoints for the MAD Phase 1b and POC Phase 2 studies.

3.1 Phase 1b MAD Study

3.1.1 Primary Endpoints

Evaluation of safety, tolerability, and immunogenicity at each dose level, to determine the optimal dose, will include the recording of the following parameters:

- Incidence and severity of AEs, AEs of special interest, and SAEs
- 12-lead ECGs
- Vital signs (blood pressure [BP], heart rate, and temperature)

- Clinical laboratory assessments
- Physical examinations
- Evaluation for ADAs

3.1.2 Exploratory Endpoints

- CCI [REDACTED]

3.1.3 Other Endpoints

- CCI [REDACTED]
- CCI [REDACTED]
- CCI [REDACTED]

3.1.4 PRO Endpoints

- CCI [REDACTED]
- CCI [REDACTED]

3.2 Phase 2 POC Study

3.2.1 Primary Efficacy Endpoint

The primary efficacy endpoint is the proportion of patients who achieve treatment response as measured by the SRI-4 at Day 210, along with a sustained reduction of oral CS (≤ 10 mg/day and \leq Day 0 dose) between Day 120 and Day 210

3.2.2 Secondary Efficacy Endpoints

The secondary efficacy endpoints are:

- The proportion of patients who achieve treatment response for the SRI-5 and SRI-6 at Day 210, along with a sustained reduction of oral CS (≤ 10 mg/day and \leq Day 0 dose) between Day 120 and Day 210
- Changes from baseline in dsDNA, ANA, SSA, SSB, RNP, Sm, APL autoantibodies, at Day 120 and Day 210
- Changes from baseline in C3 and C4 levels at Day 120 and Day 210
- Changes from baseline in the SLEDAI-2K at Day 210
- Time to BILAG A or B flare
- Changes from baseline in the CLASI at Day 210
- The proportion of patients with a BICLA response at Day 210
- The proportion of patients with CLASI response at Day 210
- Changes from baseline (percentage) in swollen joints and tender joints ACR-28 joint count
- Incidence and severity of AEs, AEs of special interest, and SAEs
- 12-lead ECGs
- Vital signs (BP, heart rate, and temperature)
- Clinical laboratory assessments

- Physical examinations and targeted physical examinations
- Evaluation for ADAs

3.2.3 Exploratory Endpoints

- CCI [REDACTED]

3.2.4 Other Endpoints

- CCI [REDACTED]
- [REDACTED]
- [REDACTED]

3.2.5 PRO Endpoints

- CCI [REDACTED]
- CCI [REDACTED]

4 STUDY PLAN

4.1 Study Design

This is a Phase 1b/2 combined, randomized, multicenter, double-blind, placebo-controlled trial to study the clinical efficacy, safety, and PK of SC doses of BOS161721 in adult patients with

moderately to severely active SLE. After successfully completing a screening phase, patients will be randomized to a specified dose of BOS161721 or placebo. The dosing schedule will be monthly.

The trial will consist of 2 studies: MAD Phase 1b, and POC Phase 2. Both studies will be double-blinded, and patients will have the same number of visits. Patients may receive a total of 7 SC monthly doses of study drug on Days 0, 30, 60, 90, 120, 150, and 180, followed by a 90-day safety follow-up visit.

SLE disease activity assessment data will be centrally reviewed by medical monitor and sponsor to ensure the scores are clinically meaningful and compliant with specific definition. The scope of responsibility includes, but is not limited to, review and confirmation of “A” and “B” BILAG system organ disease, confirmation of clinical components of the SLEDAI-2K score at screening and during the study, and cross-validation of the instruments used in this study to assess the disease being studied. Further details on the content and methods of data reports by the medical monitor and sponsor will be outlined in the Medical Data Review Plan along with the processes and procedures that will be followed.

4.1.1 Multiple Ascending Dose Phase 1b Study

The MAD study will consist of 3 cohorts:

- Cohort 1 (20 mg SC) will include 6 patients
 - 5 patients will receive BOS161721 (active group) and 1 patient will receive placebo (placebo group)
- Cohorts 2 (60 mg SC) and 3 (120 mg SC) will include 12 patients each
 - 9 patients in the active group and 3 in the placebo group

Doses selected for each of the 3 cohorts is based on a 90-day safety, tolerability, PK and PD data review from the Phase 1 SAD study (BOS161721-01) in healthy subjects. All doses selected for the MAD study are projected not to exceed the mean exposure of that achieved in the SAD study.

4.1.1.1 Dose Escalation for the MAD Study

The MAD study design is staggered, where after the 6 patients in Cohort 1 have received 2 doses and have completed 2 weeks of follow-up after the second dose, Cohort 2 begins dosing (after DMC evaluation of the safety and tolerability data from Cohort 1). Similarly, after 8 of the 12 patients in Cohort 2 have received 2 doses and have completed 2 weeks of follow-up after the second dose, Cohort 3 begins dosing after DMC evaluation of the safety and tolerability data from Cohorts 1 and 2. Each cohort will continue at their assigned dose level through their respective 6-month treatment periods (See Study Schematic, [Section 4.1](#)). If > 3 patients discontinue the study in a cohort, he/she may be replaced.

Criteria for dose escalation are further described in the DMC Charter. See [Section 4.1.1.2](#) for additional details about DLTs.

4.1.1.2 Dose Limiting Toxicity (DLT)

Severity of adverse events will be graded according to National Cancer Institute Common Terminology Criteria for Adverse Events (NCI CTCAE) version 4.03. For the purpose of dose escalation, any of the following AEs occurring after study drug administration, which are attributable to the study drug, will be considered DLTs:

Hematologic:

- Grade 4 neutropenia
- Grade 3 neutropenic infection
- Grade 3 thrombocytopenia with bleeding
- Grade 4 thrombocytopenia

Non-Hematologic:

- Grade 3 or above toxicities, persisting after optimal treatment with standard medical therapy (eg, anti-emetics, anti-diarrheals)
- Drug-induced liver injury ([DILI], Hy's Law), as defined in [Section 7.2.2.6.3](#)

Investigators should always manage their patients according to their medical judgment which may include interruption of study drug based on the particular clinical circumstances.

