Abnormal values in AST and/or ALT levels concurrent with abnormal elevations in total bilirubin level that meet the criteria outlined below in the absence of other causes of liver injury are considered potential cases of DILI, and as potential Hy's Law cases, and should always be considered important medical events. If symptoms compatible with DILI precede knowledge of serum chemical test abnormalities, liver enzyme measurements should be made immediately, regardless of when the next visit or monitoring interval is scheduled. In some cases, symptoms may be an early sign of injury and although typically less sensitive than serum enzyme elevations, they may indicate a need for prompt serum testing. An increase in liver enzymes should be confirmed by a repeated test within 48 to 72 hours following the initial test, prior to reporting of a potential DILI event. Patients will continue to have weekly or biweekly liver enzyme measurements until resolution or levels return to baseline.

All occurrences of potential DILIs, meeting the defined criteria, must be reported as SAEs (see [Section 6.2.2.7.2](#) for reporting details).

Potential DILI is defined as:

1. ALT or AST elevation $> 3 \times$ ULN

AND

2. Total bilirubin $> 2 \times$ ULN, without initial findings of cholestasis (elevated serum alkaline phosphatase)

AND

3. No other immediately apparent possible causes of ALT or AST elevation and hyperbilirubinemia, including, but not limited to, viral hepatitis, pre-existing chronic or acute liver disease, or the administration of other drug(s) known to be hepatotoxic

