APPENDIX 7 PROTOCOL SUMMARY OF CHANGES

The protocol summary of changes was moved to the end of the protocol for easier readability.

Significant changes are described in the table below. Changed text is displayed for the first major occurrence only. Deleted text is presented in strikethrough format, and added text is presented in bold format.

Section	Description of Changes	Rationale
Global	Add: Added ' Protocol Date and Version: 21 March 2018; V3.0 ' to the header.	Administrative
Global	Change: Changed Version number from V2.0 (Amendment 1) to V3.0 (Amendment 2) and Version date from 14 November 2017 to 21 March 2018 .	Administrative
Global	Change: Changed subjects to patients .	Replaced 'subjects' to 'patients' since the enrolled participants are with SLE condition
Global	Made administrative and editorial (formatting, typographical, and grammatical) updates.	Administrative
PROTOCOL SUMMARY, Background and Rationale	Add: The Phase 2 portion will be a proof of concept (POC) study, where dose selection will be based on the data monitoring committee (DMC) and sponsor's assessment of safety, tolerability, immunogenicity, and PK and PD data from the MAD study of 30 patients treated with BOS161721/placebo	Clarification that POC dose selection will be based on DMC and sponsor assessment
PROTOCOL SUMMARY, Objectives and Endpoints	The objectives and endpoints sections were combined together and are now represented in a table format in order to demonstrate which endpoints correspond to each objective. Only primary and secondary objectives and endpoints are listed within the synopsis. Additional edits were made to some objectives and endpoints. Some new endpoints were added to the study. An exploratory objective, to examine PK and PD effects of BOS161721 in subjects with mild to moderate SLE, was changed to 'secondary objective'. Changes to the objectives and endpoints are noted below: MAD Phase 1b Study	Updated for clarity and to provide a comprehensive list of endpoints identified in the protocol

Section	Description of Changes	Rationale
OBJECTIVES	ENDPOINTS	
Primary		

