	
*Additional patients may be enrolled to confirm sufficient numbers of patients are in the full analysis set (FAS).
																
	
Eligible patients will be assigned to the study phase which is active at time of enrollment. Similarly, patients in the Phase 1 MAD will be assigned to the cohort which is active. Each patient will be assigned a unique randomization number which will not be reused.
																
	
All patients, investigators, and study team participants will be blinded to treatment assignment. An independent biostatistician not otherwise involved on the study will be unblinded and prepare materials for the interim analysis (IA) and the DMC safety reviews.
																

Section Description of Changes Rationale

[figure not shown]
The DMC will review unblinded data during safety reviews and the IA. A limited team at Boston Pharmaceuticals will review unblinded results from the Phase 1b MAD portion during the IA to determine the dose that will be used for the Phase 2 POC portion of the study. Details regarding maintenance of the blinding and content of data reviews will be described in the DMC charter or related study documentation.

Section 3.3, Study Schematic

Replace:

With:

Section 3.4, Schedule of Assessments (Table 1)

Replace:

	Screen ^a	Enroll	Treatment Period		
			Follow-Up		
Days	-28 to -1	0	7 (± 1)	15 (± 3)	30 (± 3)
Visit Number	1	2	--	3	4
Injection site reaction assessment ^f		X	X		X
Plasma CCI & CCI	X	X		X	X
Whole blood for	X	X		X	X

The futility analysis was removed due to the modest size of the trial but more importantly because the least reliable data (high placebo response) is known to occur during the first half of the study (before week 24) when futility analysis was planned

Clarification of when certain assessments will be collected

Section	Description of Changes	Rationale				
	leukocyte immunophenotype					
	CCI [REDACTED]		X		X	X
	CCI [REDACTED]	X	X			X

With:

	Screen ^a	Enroll	Treatment Period Follow-Up		
			7 (± 1)	15 (± 3)	30 (± 3)
Days	-28 to -1	0	7 (± 1)	15 (± 3)	30 (± 3)
Visit Number	1	2	--	3	4
Injection site reaction assessment		X ^f	X		X
Plasma CCI [REDACTED] & CCI [REDACTED]		X		X	X
Whole blood for leukocyte immunophenotype		X		X	X
CCI [REDACTED]		X		X	
CCI [REDACTED]	X	X			X

Section	Description of Changes	Rationale
---------	------------------------	-----------

Section 3.4,
 Schedule of
 Assessments
 (Table 1)

Replace:

	Treatment Period Follow-Up			Safety Follow-up		

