4.3 Schedule of Assessments

Table 1. Schedule of Assessments - Phase 1b - Multiple Ascending Dose

	Screen ^a	Enroll	Treatment Period Follow-Up											Safety Follow-Up		
Days	-28 to -1	0	7 (± 1)	15 (± 3)	30 (± 3)	44 (± 3)	60 (± 3)	90 (± 3)	120 (± 3)	150 (± 3)	180 (± 3)	187 (± 3)	195 (± 3)	210 (± 3)	240 (± 3)	270 (± 3)
Visit Number	1	2	--	3	4	5	6	7	8	9	10	--	--	11	12	13
GENERAL ASSESSMENTS																
Informed consent	X															
Inclusion/Exclusion criteria	X															
Medical history	X															
Demographics	X															
SLICC Criteria for SLE	X															
Concomitant medication ^b	X	X	X	X	X	X	X	X	X	X	X	X	X	X	X	X
Randomization ^c		X														
BOS161721 or placebo dosing		X			X		X	X	X	X	X					
SAFETY ASSESSMENTS																
Full physical exam	X	X														
Chest x-ray ^d	X															
C-SSRS	X	X						X			X					
AEs and SAEs		X	X	X	X	X	X	X	X	X	X	X	X	X	X	X
12-lead ECG ^e	X	X			X			X								X
Injection site reaction assessment ^f		X	X		X		X	X	X	X	X	X	X	X	X	X
Targeted physical examination				X	X	X	X	X	X	X	X			X	X	X
Vital signs (BP, HR, and temperature) ^g	X	X		X	X	X	X	X	X	X	X			X	X	X
EFFICACY ASSESSMENTS																
BILAG-2004 Index	X	X			X		X	X	X	X	X			X	X	X

Table 1. Schedule of Assessments - Phase 1b - Multiple Ascending Dose

	Screen ^a	Enroll	Treatment Period Follow-Up											Safety Follow-Up		
Days	-28 to -1	0	7 (± 1)	15 (± 3)	30 (± 3)	44 (± 3)	60 (± 3)	90 (± 3)	120 (± 3)	150 (± 3)	180 (± 3)	187 (± 3)	195 (± 3)	210 (± 3)	240 (± 3)	270 (± 3)
Visit Number	1	2	--	3	4	5	6	7	8	9	10	--	--	11	12	13
SLEDAI-2K	X	X			X		X	X	X	X	X			X	X	X
PGA of disease activity	X	X			X		X	X	X	X	X			X	X	X
ACR-28 joint count	X	X			X		X	X	X	X	X			X	X	X
CLASI	X	X			X		X	X	X	X	X			X	X	X
CCI		X			X		X	X	X	X	X			X	X	X
SLICC/ACR Damage Index		X									X					
CCI		X			X		X	X	X	X	X			X	X	X
LABORATORY ASSESSMENTS																
CD4+ count	X	X		X	X	X		X			X					
Clinical laboratory assessments (hematology and clinical chemistry) ^h	X	X			X	X	X	X	X	X	X			X	X	X
Coomb's test direct ⁱ	X	X			X		X	X	X	X	X			X	X	X
Total IgG and IgM	X	X		X	X	X		X			X					
Plasma CCI	X	X			X		X	X	X	X	X			X	X	X
Plasma CCI & CCI	X	X		X	X		X	X			X					
Whole blood for leukocyte immunophenotype	X	X		X	X		X	X			X					
ADA ^j		X		X	X		X	X			X					X
nAb ^k								X			X					
pSTAT3		X			X	X	X	X			X					X
CCI		X									X					
Whole blood RNA collection		X		X	X			X								X

Table 1. Schedule of Assessments - Phase 1b - Multiple Ascending Dose

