7.2 Safety Assessments

7.2.1 Laboratory Assessments

Laboratory tests will be performed at times defined in the Schedule of Assessments (Section 4.3). Patient eligibility will be determined based on these tests at screening. Unscheduled clinical labs may be obtained at any time during the study to assess any perceived safety concerns.

A central laboratory will be used (with the exception of urine pregnancy tests and stool analysis) to ensure accuracy and consistency in test results. The central laboratory will transmit all results for protocol tests, scheduled and unscheduled, to the clinical data base. Laboratory/analyte results that could unblind the study (ie, biomarker results) will not be reported to investigative sites. Urinalysis will be performed on midstream, clean catch specimens. Some biomarkers listed above will not be drawn at some sites due to geographical logistical challenges. See the laboratory manual for details.

Endpoint analyses will be based on changes from baseline assessments at Days 120 and 210.

Table 3. Laboratory Tests

Hematology	Chemistry	Urinalysis	Other Safety Tests
Hemoglobin	BUN	pH	Spot urine for protein/creatinine ratio
Hematocrit	Creatinine	Glucose (qual)	FSH ^b
RBC count	Glucose (fasting)	Protein (qual)	Urine pregnancy test ^c
RDW	Calcium	Blood (qual)	QuantiFERON [®] -TB Gold In-Tube test (QFT-G)
MCV	Sodium	Ketones	Serology ^d (Hepatitis B and C; HIV-1/2 combination)
MCH	Potassium	Nitrites	Stool sample ^e
MCHC	Chloride	Leukocyte esterase	
Platelet count	Total CO ₂ (bicarbonate)	Urobilinogen	
WBC count	AST, ALT	Urine bilirubin	
CD4+ count	Total bilirubin	Microscopy ^a	
Total neutrophils (Abs)	Alkaline phosphatase		
Eosinophils (Abs)	Creatine kinase		
Monocytes (Abs)	Uric acid		
Basophils (Abs)	Albumin		
Lymphocytes (Abs)	Total cholesterol (fasting)		
Reticulocytes (%)	LDL-C (fasting)		
	HDL-C (fasting)		
	Triglycerides (fasting)		
	Total protein		
	PT/INR		
	Additional Tests^f (potential Hy's Law)		Immunogenicity, PD and other Biomarker Tests
	AST, ALT (repeat)		ADA
	Total bilirubin (repeat)		nAb ^g
	Albumin (repeat)		pSTAT3 (predose [trough] samples only, in Phase 2)
	Alkaline phosphatase (repeat)		Total IgG & IgM
	Direct bilirubin		Plasma CCI
	Indirect bilirubin		Plasma CCI & CCI
	GGT		Whole blood for leukocyte immunophenotype and RNA
			CCI
			CCI
			Antibodies CCI
			CRP
			Direct Coomb's test ^h

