6.3 Treatment Period/Follow-Up Visits

See Section 4.3 for allowable windows for each visit. The following procedures will be performed at every study drug administration visit (Weeks 4, 8, 12, 16, 20, and 24) and follow-up visits during the treatment period (Weeks 2 and 6):

- Targeted physical examination;
- Vital signs (prior to PK blood draw);
- Concomitant medication documentation;
- Documentation of AEs and SAEs (see [Section 7.2.2.5](#) on SAE reporting requirements).

The following assessments will be performed only at Weeks 4, 8, 12, 16, 20, and 24:

- PROs: **CCI** [REDACTED];
- Urine pregnancy tests will be collected on WOCBP prior to study drug administration;
- Injection site reaction assessments will be performed predose and 2 hours postdose;
- Direct Coomb's test (if indicated);
- Spot urine for protein to creatinine ratio;
- Urinalysis;
- **CCI** [REDACTED];
- Plasma **CCI** [REDACTED];
- PGA, BILAG-2004 Index, SLEDAI-2K, ACR-28 joint count, and the CLASI will be completed.
- In addition the following assessments will be completed:

- SLICC/ACR Damage Index will be completed at Week 24 (Visit 10).
- C-SSRS will be completed at Weeks 12 and 24 (Visits 7 and 10);
- ECGs will be performed at Weeks 4 and 12 (Visits 4 and 7) prior to PK blood draw.
- See [Table 1](#) and [Table 2](#) for details of PK sampling in the MAD and POC studies, respectively.
- Hematology and chemistry assessments will be performed at Weeks 4 and 6 (Visits 4 and 5) for the MAD study, only, and at Weeks 8, 12, 16, 20, and 24 (Visits 6 through 10) for both studies.
- The CD4+ count and total IgG and IgM levels will be assessed at Weeks 2, 4, 6, 12, and 24 (Visits 3, 4, 5, 7, and 10).
- Plasma **CCI** & **CCI**, ADA, and whole blood for leukocyte immunophenotype will be assessed at Weeks 2, 4, 8, 12, and 24 (Visits 3, 4, 6, 7, and 10).
- pSTAT3 will be assessed at Weeks 4, 6, 8, 12, and 24 (Visits 4, 5, 6, 7, and 10).
- Whole blood RNA will be collected at Weeks 2, 4, and 12 (Visits 3, 4, and 7).
- CRP will be measured at Week 12 (Visit 7), and nAb will be assessed if patient is positive for ADA at Weeks 12 and 24 (Visits 7 and 10).
- **CCI** will be assessed at Week 24 (Visit 10).

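### In the latest Phase 1b schedule shown, no neutrophil, platelet or liver value is scheduled between Day 0 and the Day 30 second dose; if the current table is the same, adding them to the Day 15 draw is a cheap improvement

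*Protocol*

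**What the plan says.** The file holds the back part of Version 3.0 (Amendment 2) and the text of Versions 2.0 and 1.0. The current Sections 3.1.1.2 and 3.4 lie in a part that is not shown, so Version 2.0 gives the latest DLT definition and Phase 1b schedule available.

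- **DLTs (V2.0, Section 4.1.1.2).** For the purpose of escalation, "any of the following AEs occurring after study drug administration, which are attributable to the study drug, will be considered DLTs". Three listed items are laboratory-defined: Grade 4 neutropenia, Grade 4 thrombocytopenia and Hy's Law injury. Under Section 4.1.1.3, two or more DLTs halt further dosing in the cohort.
- **Schedule (V2.0, Section 4.3, Table 1).** The row beginning "Clinical laboratory assessments (hematology and clinical chemistry" is marked at screening and on Days 0, 30, 44 and later. Days 7 and 15 are blank. Dosing is on Days 0, 30, 60, 90, 120, 150 and 180.
- **Version 1.0 text (Section 6.3)** agrees: "Hematology and chemistry assessments will be performed at Weeks 4 and 6 (Visits 4 and 5) for the MAD study, only".
- **Laboratory (V2.0, Section 7.2.1).** "A central laboratory will be used (with the exception of urine pregnancy tests and stool analysis"; no turnaround time is given. Also: "Unscheduled clinical labs may be obtained at any time during the study to assess any perceived safety concerns".
- **Liver rules (V3.0, Section 6.2.2.6.3).** "An increase in liver enzymes should be confirmed by a repeated test within 48 to 72 hours following the initial test". Symptoms call for immediate testing, and certain combinations of liver values make stopping mandatory.
- **Change log (V3.0, Appendix 7).** It itemises Table 1 changes to the injection site, plasma marker, immunophenotype and pSTAT3 rows and to footnotes, and lists none for the hematology and chemistry row. It covers significant changes, and "Changed text is displayed for the first major occurrence only". Its Table 1 extract still marks "Whole blood for leukocyte immunophenotype" on Day 15.

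**The concern.** A laboratory-defined DLT can be acted on only when a laboratory value exists. In the schedule shown, the first neutrophil, platelet and liver values after dose 1 are drawn at the visit where dose 2 is given. Unless the central laboratory returns Day 30 results before the injection, the second dose is given with nothing scheduled since Day 0.

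The early safeguards do not close this gap. An unscheduled test needs someone to perceive a concern, and an immediate liver test needs symptoms. A silent abnormality triggers neither.

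A subcutaneous antibody dose cannot be withdrawn, and Section 1.2.3 (V2.0) gives a terminal half-life of 44 days. At stake are the individual patient's second dose and how early the two-DLT halt can operate.

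**Working it through.** There is no sample-size or power figure to reproduce. The check reads the table, works out the timing, and asks whether the benefit can be sized.

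**1. Table alignment (V2.0 Table 1, 16 columns).**
- Panel: screening, Days 0, 30, 44, 60, 90, 120, 150, 180, 210, 240, 270.
- Dosing: Days 0, 30, 60, 90, 120, 150, 180.
- Panels strictly between dose 1 and the dose 2 visit: 0. With Day 15 added: 1.
- Panels up to the Day 44 escalation point: 2 (Days 30 and 44). With Day 15 added: 3.
- Already drawn on Day 15: CD4+ count, IgG and IgM, ADA, immunophenotype, RNA and PK. CD4+ sits under Hematology in Table 3, so the accurate statement is no neutrophil, platelet or liver value, not no hematology at all.

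**2. Timing (both visits have a window of ±3 days).**
- Day 15 visit: Days 12 to 18. Day 30 visit: Days 27 to 33.
- Lead time of a Day 15 panel over dose 2: shortest 27 − 18 = 9 days, longest 33 − 12 = 21 days.
- A 72-hour repeat after the latest Day 15 draw ends on 18 + 3 = Day 21, which is 27 − 21 = 6 days before the earliest dose 2.
- A liver rise first found on Day 30 is repeated on Day 32 or 33, after a dose given on Day 30.

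**3. Exposure.** Inputs from V2.0 Sections 1.2.2.3 and 1.2.3: median Tmax 6 days, half-life 44 days (range 42 to 46). With simple exponential decline, the share of the Day 6 level left on Day 30 is 0.5^(24/44) = 0.69, and 0.67 to 0.70 over the range. Dose 2 is added to about two thirds of the first peak.

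**4. Can the benefit be sized?** Only by assuming an onset pattern and a duration d, and the documents give neither. Take uniform onset, and count an event as detected if it is present on a test day.

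| Assumed d (days) | Seen by Day 44, panels on 30 and 44 | Seen by Day 44, with Day 15 | Gain (points) | Seen on Day 15, onset Days 0 to 30 |
|---|---|---|---|---|
| 7 | 14/44 = 32% | 21/44 = 48% | 16 | 7/30 = 23% |
| 14 | 28/44 = 64% | 42/44 = 95% | 32 | 14/30 = 47% |
| 21 | 35/44 = 80% | 44/44 = 100% | 20 | 15/30 = 50% |
| 30 | 44/44 = 100% | 44/44 = 100% | 0 | 15/30 = 50% |

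The last column is min(d, 15)/30. Its counterpart under the schedule shown is 0%, unless Day 30 results are back before the injection. The Day 44 gain runs from 0 to 32 points according to d alone, and nothing in the documents selects d. The table shows dependence on the assumptions; it is not an estimate.

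**The case against.** **The schedule is superseded.** This stands as a condition. The Version 3.0 table may differ. Its log itemises row changes and lists none here, but it is limited to significant changes, so persistence is likely, not confirmed. As read from the PDF, the Version 1.0 table seems to mark this row on Day 15. The ECG row in the same table falls on Days 15 and 60, against Weeks 4 and 12 in the Version 1.0 text, so those rows are shifted. The Version 1.0 text puts the panel at Weeks 4 and 6.

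**DLTs are defined for escalation, and escalation is covered.** Correct. A reader might infer that the monitoring committee escalates without post-dose laboratory data. It does not: Section 4.1.1.1 (V2.0) places the review after two weeks of follow-up from dose 2, so the Day 30 and Day 44 panels come first. What remains is the timing of dose 2 in each patient. Investigators may interrupt the drug on their own judgment, but only with a reason to do so.

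**The pharmacokinetics argue against short events.** An effect that follows exposure would probably last to Day 30, and at d = 30 the Day 44 gain is zero. That rules out claiming a detection gain. It does not remove the point, because a lasting effect that began near the Day 6 peak would be visible on Day 15, before dose 2.

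**Prior risk is low.** The single-dose study reached 240 mg with no clinically relevant laboratory changes, though in healthy subjects without concomitant medication. The first month is also better covered by earlier data than the accumulation phase, which this change leaves as it is.

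**An extra panel can mislead.** Patients may enter with a neutrophil count of 500/mm³ or slightly more, and may take azathioprine, mycophenolate or methotrexate. Background dips will appear, and Cohort 1 has only 6 patients under a two-DLT halt. Attribution must come before counting.

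**Conclusion.** The point holds as a conditional, low-cost improvement. In the latest Phase 1b schedule shown, no neutrophil, platelet or liver value is scheduled between Day 0 and the dose 2 visit, while three DLTs can be silent and the early safeguards depend on a perceived concern.

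Two stronger readings are not supported. The documents do not show an error or contradiction in the current protocol, because its table is not available here. Nor do they support any percentage for missed events, because onset and duration are not given and the turnaround of Day 30 results is not stated. What is firm is the timing: a Day 15 result can be repeated and judged at least 6 days before dose 2, and a Day 30 result cannot be confirmed before a dose given that day.

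**What to change.** Check Table 1 in Section 3.4 of the current protocol. If hematology and chemistry are still unmarked on Day 15:

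- Add hematology with differential and platelets, plus liver chemistry, to the blood draw already made on Day 15.
- Exempt that draw from the fasting glucose and lipid panel in footnote h.
- Require the result to be reviewed before dose 2.
- State that an abnormal value must be attributed before it counts toward the two-DLT halt. Version 2.0, Section 7.2.2.1 already keeps non-serious results due to SLE activity out of the adverse event record.

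No visit, venepuncture or DLT threshold changes. The cost is one or two tubes and the assays for about 30 patients (6 + 12 + 12), an edit to one row and one footnote, a short pre-dose check, and the work of attributing background lupus- or immunosuppressant-related dips. The change protects dose 2 only; the same-day panels on Days 60, 90, 120, 150 and 180 stay as they are.
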